#### **6.4. Other Eligibility Criteria**

To assess any potential impact on subject eligibility with regard to safety, the investigator must refer to the RVT-101 Investigator Brochure for detailed information regarding warnings, precautions, contraindications, AEs, and other significant data pertaining to the investigational product(s) being used in this study.

Eligibility review by Axovant or its representative(s) may be undertaken for select subjects.

#### **6.5. Screening Failures**

Screen Failures are defined as subjects who sign an informed consent form (ICF) for RVT-101-2001 but are never subsequently randomized and who do not enter the Single-Blind Run-In Phase. A minimal set of screen failure information is required including demography, screen failure details, eligibility criteria, and any serious adverse events (SAEs).

Subjects who are screen failures may be rescreened only after approval by the study Medical Monitor.

#### **6.6. Withdrawal Criteria**

##### **6.6.1. Reasons for Withdrawal**

A withdrawal from the study is defined as withdrawing any time after entering the Single-Blind Run-In Phase and before completion of the Week 24 Visit (Visit 12). Subjects who permanently discontinue use of investigational product (IP) will be considered to be withdrawn from the study and will not be allowed to rescreen. Subjects may withdraw from the study at any time and for any reason. The investigator (or designee) must document the reason for withdrawal in the electronic case report form (eCRF). Information related to AEs will continue to be collected as per usual procedures on subjects who have discontinued IP. Withdrawn subjects will not be replaced. The reasons for subject withdrawal will be recorded and may include, but are not limited to:

- Any clinical AE, laboratory abnormality, or other medical condition or situation occurs such that continued participation in the study would not be in the best interest of the subject in the opinion of the investigator.
- Pregnancy of female subject (discontinuation of treatment, but will be followed until the outcome of pregnancy is known)
- Significant protocol violation
- Subject requests to discontinue for any reason; it is important to determine whether the withdrawal of consent is primarily due to an AE, lack of efficacy, or other reason.
- Sponsor decision to withdraw the subject or terminate the study, if it is considered in the best interest of the subject or study.

The above reasons do not automatically lead to withdrawal from the study in all cases. The final decision will be based on consultation between the principal investigator and the study Medical Monitor, with the ultimate decision by the principal investigator, subject or caregiver, except in cases where the Sponsor decides to terminate the study or withdraw the subject from the study.

If a subject meets discontinuation criteria during treatment, an Early Termination Visit will be required ([Section 6.6.2](#)).

### **6.6.2. Subject Withdrawal Procedures**

If a subject is prematurely discontinued from treatment with the IP, the investigator must make every effort to perform the evaluations scheduled for the Early Termination Visit ([Table 2](#)). In the case where the subject permanently discontinues study medication between scheduled clinic visits he/she should be recalled to the clinic as soon as possible and preferably within 7 days of stopping study medication for the Early Termination Visit.

**Lost to follow-up:** If a subject is lost to follow-up, every effort must be made by study center personnel to contact the subject, inquire about the reason for discontinuation/withdrawal, and follow up with any unresolved AEs/serious adverse events (SAEs). A minimum of 3 attempts at contact should be made and recorded in the subject's source documentation, with 1 contact being by certified letter. All measures taken to contact the subject and information received during those attempts must be documented.

## 7. STUDY TREATMENT

### 7.1. Investigational Product and Other Study Treatment

IP in this study is defined as 35 mg RVT-101 tablets and their matching placebo, and will be provided by Axovant Sciences. RVT-101 and placebo tablets will be indistinguishable from each other. All subjects will take two tablets of IP daily at bedtime, one from each supplied bottle, with or without food; this will consist of either two tablets of 35 mg RVT-101, one tablet of 35 mg RVT-101 and one tablet of placebo, or two tablets of placebo.

IP for the Single-Blind Run-In Period (Weeks -2 to 0) will be supplied at Visit 2. Subjects will be given an IP kit containing 2 bottles of placebo tablets. Each bottle will contain 50 tablets, which is sufficient medication for 2 weeks plus 36 days overage. Subjects will be instructed to take two tablets of IP daily at bedtime with or without food; this will consist of one tablet from each of the two bottles supplied. In the event that the Single-Blind Run-In period is extended to repeat the MMSE, no new IP will be dispensed. Drug accountability will be checked, and subjects will be re-dispensed study medication kit and bottles they received at Visit 2.

Product name:	RVT-101	Placebo
Formulation description:	pink, film-coated, round tablets	pink, film-coated, round tablets
Dosage form:	35 mg Tablet	Placebo Tablet
Unit dose strength(s)/ Dosage level(s):	35 mg 35 mg or 70 mg	N/A placebo
Route of Administration:	Oral	Oral
Duration (Run-in Period):	N/A	2 weeks
Duration (Treatment Period):	24 weeks	24 weeks
Dosing instructions:	Take before bedtime with or without food	Take before bedtime with or without food
Manufacturer/Source of Procurement	Metrics Contract Services Greenville, NC or Catalent Pharma Solutions Kansas City, MO	Metrics Contract Services Greenville, NC or Catalent Pharma Solutions Kansas City, MO

IP for the Double-Blind Treatment Period (Weeks 0 to 24) will be supplied at Visits 3, 6, 8, 10, and 11. At each dispensing visit during the Treatment Period, subjects will be given an IP kit containing 2 bottles of IP. Depending on treatment assignment, subjects will receive either two bottles of 35 mg RVT-101 tablets, one bottle of 35 mg RVT-101 tablets and one bottle of placebo tablets, or two bottles of placebo tablets. Each bottle will contain 50 tablets, which is sufficient for 4 weeks plus 22 days overage (V3, V6, V8) and for 6 weeks plus 8 days overage (V10 and V12). Subjects will be instructed to take two tablets of IP daily at bedtime with or

without food; this will consist of one tablet from each of the two bottles in the kit. New bottles of IP will not be dispensed at Visits 4, 5, 7, and 9, however, drug accountability will be checked, and subjects will be re-dispensed the IP bottles they received at the previous dispensing visit. All subjects and their caregivers should be instructed to bring IP bottles, with any unused drug, to each visit. It is important that drug accountability is checked individually for each of the two dispensed bottles.

## 7.2. Randomization/Treatment Assignment

Subjects will be assigned to receive 35 mg RVT-101, 70 mg RVT-101, or placebo in accordance with the randomization schedule, prior to the start of the Double-Blind Treatment Period, using validated software.

Following confirmation of eligibility at the end of Single-Blind Run-In Period, subjects will be randomized to placebo or 35 mg RVT-101, 70 mg RVT-101 in a 1:1:1 ratio. Randomization will be stratified according to Baseline MMSE score in the groupings of 14-17 points, 18-21 points and 22-26 points and according to whether subjects are or are not taking a cholinesterase inhibitor as a concomitant medication.

## 7.3. Blinding

This will be a double-blind study. The study will include a 2-week Single-Blind Run-In Period during which investigators will know that the subject is taking placebo but the subject/caregiver will not. This will be followed by a 24-week Double-Blind Treatment Period when neither subjects nor investigators will know which of the three treatments the subject is receiving. Subjects will be informed that they will receive placebo at some point during the study but they will not know when this will be. Subjects will not be informed of transition from the Single-Blind Run-In Period to the Double-Blind Treatment Period. RVT-101 and placebo will be provided as tablets that are indistinguishable in appearance, smell, and taste.

The following will apply:

- The investigator or treating physician may unblind a subject's treatment assignment. Such a measure should be taken **only in the case of an emergency** OR in the event of a serious medical condition when knowledge of the IP is essential for the appropriate clinical management or welfare of the subject as judged by the investigator.
- In the event that a medical emergency or condition requires knowledge of the subject's treatment assignment, the investigator will access the interactive voice response system (IVRS)/interactive web response system (IWRS) to obtain the treatment assignment for that subject. The procedure of unblinding for a specific subject is provided in the IVRS/IWRS manual.
- The investigator must inform the Medical Monitor about the unblinding as soon as possible, but without revealing the treatment assignment of the unblinded subject.

- The sponsor will be informed without delay of the decision to unblind any subject and will determine whether any additional measures need to be taken for the safety of subjects currently in the study.
- Any other requests to reveal a subject's treatment identity must be requested of, and approved by, Axovant Sciences.
- A subject will be withdrawn from the study if his or her treatment code is unblinded by the investigator or treating physician. The date and reason for the unblinding must be fully documented in the eCRF.

Axovant Sciences or their designee may unblind the treatment assignment for any subject if this is required to fulfill regulatory reporting obligations such as expedited SAE reporting.

#### **7.4. Packaging and Labeling**

RVT-101 35 mg tablets and matching placebo tablets will be packaged in high-density polyethylene bottles. Subjects will receive an IP kit consisting of two bottles at each IP dispensing visit. The IP kit and the individual bottles will be labeled.

Labels for IP kits and for RVT-101 and placebo bottles will meet all applicable requirements of the US Food and Drug Administration (FDA) and Annex 13 of Good Manufacturing Practices: Manufacture of investigational medicinal products (July 2010) and/or other local regulations as applicable.

The label for the IP will contain at a minimum the following information for the US (additional items will be added as required for other study countries):

- Protocol number
- Lot number
- Kit or bottle identification number
- Quantity
- Dosing directions
- “Caution: New Drug – Limited by Federal law to investigational use”

#### **7.5. Preparation/Handling/Storage/Accountability**

No special preparation of IP is required. IP will be stored at room temperature (15 - 30°C) and protected from light.

- Only subjects enrolled in the study may receive IP and only authorized site staff may supply or administer IP. All IP must be stored in a secure, environmentally controlled and monitored (manual or automated) area in accordance with the labelled storage conditions, with access limited to the investigator and authorized site staff.

- The investigator, institution, or the head of the medical institution (where applicable) is responsible for IP accountability, reconciliation, and record maintenance (i.e., receipt, reconciliation, and final disposition records).
- Site staff will record the subject number on the packaging labels for the kit and each bottle dispensed.
- Further guidance and information for final disposition of unused IP are provided in the pharmacy manual.
- Under normal conditions of handling and administration, IP is not expected to pose significant safety risks to site staff. In the case of unintentional occupational exposure, notify the monitor, Medical Monitor, and/or the Axovant Sciences study contact.
- A Material Safety Data Sheet/equivalent document describing occupational hazards and recommended handling precautions either will be provided to the investigator, where this is required by local laws, or is available upon request from Axovant Sciences.

## **7.6. Compliance with Investigational Product Administration**

When subjects are dosed at the site, they will receive IP directly from the investigator or designee, under medical supervision. The date and time of each dose administered in the clinic will be recorded in the source documents. The dose of IP and study subject identification will be confirmed at the time of dosing by a member of the study site staff other than the person administering the IP.

Subjects and caregivers should be instructed that subjects are to take one tablet of IP from each bottle before bedtime. Subjects and caregivers must be made aware that subjects are not to take two tablets from the same bottle, and are not to combine pills from the two bottles into a single storage bottle. The contents of each bottle must remain distinct. Product administration instructions should be reinforced at each visit.

Every effort should be made to encourage subject compliance with the dosage regimen as per protocol for IP. The investigator is responsible for discussing methods to ensure high treatment compliance with patients and caregivers before randomization. All subjects and their caregivers should be instructed to return IP bottles with any unused drug at each visit to the investigator or designee. A record of the supplies dispensed, taken, and returned will be made in the eCRF at each visit. The investigator or designee is responsible for reconciling the number of tablets returned with the expected number of tablets to be taken by a study subject and accounting for any discrepancies for each of the two bottles.

Subjects should be withdrawn from the study where there has been a failure to take blinded IP for a period exceeding 7 consecutive days. While interruptions in IP administration should be avoided wherever possible, short-term interruptions ( $\leq 7$  days) due to forgetfulness, caregiver

illness or absence, a pause in IP administration required during an intervention, hospitalization, or while a subject considers the study continuation, or for any other reason are not grounds for automatic withdrawal but should be assessed by the investigator.

Other major protocol violations as well as use of excluded drugs (see [Section 7.9.2](#)) may be cause for discontinuation of IP or withdrawal from the study.

## **7.7. Treatment of Investigational Product Overdose**

Any dose of RVT-101 greater than 105 mg within a 24-hour time period will be considered an overdose.

No data are available with regard to overdose of RVT-101 in humans. There is no specific treatment to be used in the event of overdose with RVT-101. Investigators should use their clinical judgment in treating cases of overdose as dictated by the subject's clinical status.

In the event of an overdose the investigator or treating physician should:

- Contact the Medical Monitor immediately,
- Closely monitor the subject for AEs/SAEs and laboratory abnormalities and ensure appropriate clinical management. Overdose in the absence of other AEs will not be reported as an AE in its own right.
- Obtain a plasma sample for PK analysis within 2 days of the overdose of IP, if requested by the Medical Monitor (determined on a case-by-case basis), and
- Document the quantity of the excess dose as well as the time of administration of the overdose in the eCRF.

It is not necessarily required that the investigator unblind a subject who has taken an overdose. As noted in [Section 7.3](#), unblinding should only be done in the case of an emergency OR in the event of a serious medical condition when knowledge of the investigational product is essential for the appropriate clinical management or welfare of the subject, as judged by the investigator. Decisions regarding dose interruptions will be made by the investigator in consultation with the Medical Monitor based on the clinical evaluation of the subject.

## **7.8. Treatment after the End of the Study**

The investigator is responsible for ensuring that consideration has been given to the post-study care of the subject's medical condition.

After completion of Visit 12, the subject may be considered for enrollment in the extension study RVT-101-2002. Only subjects who do not enroll in the extension study will complete the Follow-up Visit (Visit 13).

## **7.9. Concomitant Medications and Non-Drug Therapies**

### **7.9.1. Permitted Medications and Non-Drug Therapies**

All concomitant medications and those taken within 6 months prior to Screening, including over-the-counter and herbal remedies, will be recorded in the eCRF. Non-medication therapies related to the subject's DLB (e.g. neurostimulation, cognitive rehabilitation) that have occurred in the 12 months prior to Screening must also be recorded. The name of the drug, the dose, indication and route of administration as well as the dates administered should be documented; the minimum requirement is to record the drug name and dates of administration. Any medication not specified in the list of prohibited and conditional medications provided in [Table 1](#) is permitted during the study.

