Target Population	
Adult subjects aged 50 to 85, inclusive, with a diagnosis of probable dementia with Lewy bodies (DLB), in accordance with Consensus criteria (McKeith, 2005).
 
Subjects included in the study may or may not be receiving other treatments (such as cholinesterase inhibitors and/or memantine) for DLB. If subjects are taking other treatments for dementia and/or hallucinations associated with DLB, the treatment regimen must have been at a stable dose for at least 30 days, and be expected to remain stable during the study.

Number of Subjects Planned	
Approximately 240 randomized subjects
 
RVT-101 70 mg: 80 subjects
 
RVT-101 35 mg: 80 subjects
 
Placebo: 80 subjects

Number of Study Centers Planned	
Approximately 40-50

Study Design	
This is a multi-center, double-blind, randomized, placebo-controlled, parallel-group study in patients with probable DLB. The efficacy and safety of RVT-101 at doses of 70 mg and 35 mg daily will be evaluated over a 24-week treatment period in subjects with probable DLB with or without existing background DLB therapy. All subjects who are on stable doses of other background therapies for dementia and/or hallucinations associated with DLB will continue those regimens unchanged for the duration of the study. Subjects who are not on background DLB therapies at the time of screening will also be eligible for participation. All subjects will refrain from starting additional DLB treatments during the course of the study. The randomization ratio will be 1:1:1 (70 mg RVT-101: 35 mg RVT-101: placebo).
 
Randomization will be stratified according to Baseline MMSE score in the groupings of 14-17 points, 18-21 points and 22-26 points and according to whether subjects are or are not taking a cholinesterase inhibitor as a concomitant medication.
 
During double-blind treatment, there will be weekly clinical assessments for the first two weeks of treatment, bi-weekly assessments until Week 12 and every six weeks thereafter. For certain visits, subjects may have the option of whether to have assessments performed at the clinical study site or by a trained, visiting nurse in their own home.
 
An independent Safety Monitoring Committee (SMC) will review interim safety data accumulated after approximately 30 subjects have

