	
completed 4 weeks of double-blind treatment and throughout the study at points specified in the SMC Charter. The SMC will provide their recommendation regarding the acceptability of reducing the visit frequency by skipping certain visits for both newly enrolled subjects and subjects active in the study at the time of the SMC recommendation. Study enrollment will not be stopped or slowed to wait for the SMC recommendation and will proceed as planned with all visits until the SMC recommendation is made.

Duration of Treatment	
Study participation will last approximately 32 weeks: 0 to 28 days for Screening, a 2-week Single-Blind Run-In Period to evaluate baseline status, a 24-week randomized Treatment Period and a 2-week Safety Follow-up Period for subjects who do not enter the extension study.

Criteria for Evaluation	
Primary efficacy endpoint: The primary efficacy endpoint will be an assessment of motor function at Week 24. Change from Baseline to Week 24 in motor function will be measured by the UPDRS-III.
 
Secondary efficacy endpoints: Cognition will be measured by the ADAS-Cog 11 and global function by the CIBIC+ as the secondary endpoints.
 
Safety evaluation: Safety will be evaluated based on adverse events (AEs), physical examinations, vital signs (including measurements of orthostatic changes in blood pressure [BP] and heart rate [HR]), a questionnaire evaluating the occurrence of symptoms potentially associated with orthostasis, electrocardiograms (ECGs), the Columbia-Suicide Severity Rating Scale (C-SSRS) and routine clinical laboratory assessments.

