Clinical studies have suggested that 5-HT2a serotonin receptor antagonists may be useful in the treatment of the motor symptoms of Parkinson's Disease. Ritanserin, a mixed 5-HT2a/c receptor antagonist, has been shown to reduce bradykinesia and improve gait in PD patients ([Henderson et al., 1992](#)), as well as ameliorate neuroleptic-induced parkinsonism ([Bersani et al., 1990](#)). This premise is further supported by the results of a recent interim analysis of the pre-specified primary endpoint of the first 11 completers of a cross-over study of nelotanserin, a 5-HT2a receptor inverse agonist in patients with DLB. The mean change from baseline in the UPDRS Parts II + III exhibited statistically significant improvements (p-value < 0.05) for nelotanserin relative to placebo at 4 weeks ([Press Release: Nelotanserin Interim Analysis](#)).

The primary objective of this study is to assess the effects of 35-mg and 70-mg doses of RVT-101 compared with placebo on the primary endpoint of motor function as measured by the Unified Parkinson's Disease Rating Scale – Part III (UPDRS-III). The UPDRS-III is a gold standard measurement for capturing pharmacologic effects on parkinsonian motor symptoms. The secondary objectives are to assess the effects of RVT-101 compared to placebo on cognition as measured by the ADAS-Cog 11 and global function as measured by the CIBIC+.

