## **5. STUDY DESIGN**

### **5.1. Overall Design**

This is a multi-center, double-blind, randomized, placebo-controlled, parallel-group study in patients with probable DLB who are either not receiving therapy for DLB or are receiving a stable regimen of standard therapy for DLB. The efficacy and safety of RVT-101 at doses of 70 mg and 35 mg daily will be evaluated over a 24-week treatment period. All subjects who are on stable doses of other therapies to treat cognitive deficits and/or hallucinations associated with DLB will continue to remain on them for the duration of the study. Approximately 240 subjects will be randomized. The randomization ratio will be 1:1:1 (70 mg RVT-101: 35 mg RVT-101: placebo). The primary endpoint will be measured after 24 weeks of treatment. Study participation will last approximately 32 weeks: 0 to 4 weeks for Screening, a 2-week Single-Blind Run-In Period to evaluate baseline status, a 24-week randomized, double-blind, placebo-controlled Treatment Period and a 2-week Safety Follow-up Period for subjects who do not enter the extension study RVT-101-2002.

There will be weekly clinical assessments for the first two weeks of double-blind treatment, bi-weekly assessments thereafter until 12 weeks post-randomization and every six weeks thereafter. For certain visits (Visits 5, 7 and 9), subjects may have the option of whether to have assessments performed at the clinical study site or by a trained, visiting nurse in their own home.

[figure not shown]
An independent Safety Monitoring Committee (SMC) will review interim safety data accumulated after approximately 30 subjects have completed 4 weeks of double-blind treatment and throughout the study at points specified in the SMC Charter. The SMC will provide their recommendation regarding the acceptability of reducing the visit frequency by omitting certain visits (Visits 5, 7 and 9) for both newly enrolled subjects and subjects active in the study at the time of the recommendation. Study enrollment will not be stopped or slowed to wait for SMC's recommendation and will proceed as planned with all visits until the SMC recommendation is made. Site will be formally notified of the SMC's recommendation regarding whether or not Visits 5, 7 and 9 can be omitted.

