## 6. SUBJECT POPULATION

### 6.1. Type and Number of Subjects

Approximately 240 subjects with probable DLB who are either not receiving therapy for DLB or who are taking a stable regimen of therapy(ies) for DLB will be enrolled.

In order to manage the total study enrollment, Axovant Sciences, may suspend screening and/or enrollment at any site or study-wide at any time.

With the exception of the determination required in inclusion criterion #1, all study assessments and determinations may be delegated by the investigator to a suitably qualified designee approved and documented for this study. Medical decisions must be made by a qualified physician. If the investigator is not a physician, he/she must delegate medical decisions to a qualified physician and consult a physician for medical issues related to eligibility.

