- 3) If the subject is currently receiving any of the following medications, the treatment regimen has been stable (i.e., no changes in the type of drug, dose or frequency of dosing) for at least 30 days prior to the Screening Visit and there is no intent to change this treatment regimen for the duration of the study.
  - Acetylcholinesterase inhibitors (i.e., donepezil, galantamine, rivastigmine, tacrine)
  - Memantine
  - Axona® (caprylidene)
  - Antidepressants (other than MAO inhibitors)
  - Thyroid hormones
  - Atypical antipsychotics (e.g., quetiapine); Note: Clozapine is allowed, but must be stable for at least 5 months prior to Screening. In addition, the subject must not have had any episodes of neutropenia or severe infections since starting clozapine as confirmed by the clozapine-prescribing physician and must follow the clozapine prescribing information with regards to monitoring of white blood cell count.
  - Benzodiazepines and other sedatives/hypnotics  
Note: Intermittent (as needed) use of benzodiazepines and other sedative/hypnotics is allowed only if the drug has a half-life of less than 6 hours and it is not taken within 5 half-lives prior to cognitive testing.
- 4) Subject is 50 to 85 years of age, inclusive, at the time of the Screening Visit.
- 5) Female subjects must be:
  - a) Of non-childbearing potential (i.e., any female who is post-menopausal [greater than 1 year without menstrual period in the absence of hormone replacement therapy]) or surgically sterile; or,
  - b) If pre-menopausal or menopausal for 1 year or less, must have a negative pregnancy test and must not be lactating at Screening. Female subjects of childbearing potential and who are sexually active are required to practice highly effective methods of birth control during the course of the study. Female subjects for whom menopausal status is in doubt, in the opinion of the investigator, will be required to use a highly effective form of birth control. Highly effective forms of birth control are defined as methods that have a failure rate of less than 1% per year when used correctly and consistently and include:.

- combined (estrogen and progestogen containing) hormonal contraception associated with inhibition of ovulation; oral, intravaginal, or transdermal
  - progestogen-only hormonal contraception associated with inhibition of ovulation; oral, injectable, or implantable
  - intrauterine device (IUD)
  - intrauterine hormone-releasing system ( IUS)

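### L-dopa, dopamine agonists and permitted MAO-B inhibitors have no stated pre-Screening stability window although UPDRS-III is primary: a small source of extra variance, cheaply closed

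*Protocol*

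**What the plan says.** Protocol 3.2 gives the reason for the primary endpoint: "The UPDRS-III is a gold standard measurement for capturing pharmacologic effects on parkinsonian motor symptoms".

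Background drugs are controlled in several places:

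- **Inclusion criterion 3 (Protocol 6.2)** opens with "If the subject is currently receiving any of the following medications, the treatment regimen has been stable" and sets 30 days before Screening. The list is cholinesterase inhibitors, memantine, Axona, antidepressants other than MAO inhibitors, thyroid hormones, atypical antipsychotics, and benzodiazepines or other sedatives.
- **Table 1 (Protocol 7.9.2)** repeats these classes as conditional. Its prohibited column bars MAO inhibitors but exempts selective MAO-B inhibitors such as rasagiline, with no stability condition.
- **Exclusions 22 and 23 (Protocol 6.3)** set 2-month windows for cognitive rehabilitation and neurostimulation.
- **Protocol 7.9.1** supplies the default: "Any medication not specified in the list of prohibited and conditional medications provided in [Table 1](#) is permitted during the study".
- **Protocol Summary**: the 30-day sentence concerns "other treatments for dementia and/or hallucinations associated with DLB, the treatment regimen must have been at a stable dose for at least 30 days". The Study Design entry adds: "All subjects will refrain from starting additional DLB treatments during the course of the study".
- **Protocol 6.1** describes subjects "who are either not receiving therapy for DLB or who are taking a stable regimen of therapy(ies) for DLB will be enrolled". **Section 5.1** also refers to stable standard therapy for DLB, but its instruction to stay on treatment covers "other therapies to treat cognitive deficits and/or hallucinations associated with DLB".

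In the analysis, both UPDRS populations (Protocol 10.3.1, SAP 7.4) exclude subjects because of an anti-parkinsonian start or increase only where the total daily dose at Week 24 is above that at Baseline. SAP 7.4 names L-dopa, dopamine agonists and MAO inhibitors as examples. The MMRM in SAP 9.3.1 has no term for anti-parkinsonian use. The using/not-using subgroup in SAP 7.8 has no classification date.

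**The concern.** The drugs that act most directly on the primary endpoint are the ones without a stated window, while thyroid hormone needs 30 stable days. The sponsor clearly regards these drugs as able to distort UPDRS-III, because it built two analysis populations around them. That care starts at Baseline and does not reach back before it.

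If a subject's response to a recently started or increased motor drug is still developing at Baseline, the rest of that response is counted as change on study treatment. At stake is the precision of the UPDRS-III comparison, and so its power.

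**Working it through.** **1. Is there a window elsewhere?** For each route, does it fix a duration and reference date for L-dopa, dopamine agonists or MAO-B inhibitors?

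- Criterion 3 and Table 1 conditional column: 30 days, but these classes are not listed.
- Summary 30-day sentence: limited to dementia and hallucinations.
- Sections 5.1 and 6.1: a stable DLB regimen, with no duration, drug list or reference date.
- Summary bar on additional DLB treatments: reasonably reaches a new start after Screening, but not a start before it, and does not mention dose changes.
- UPDRS populations: compare Week 24 with Baseline. If the change was complete by Baseline and the dose then held, the two are equal and the subject stays in.
- Per-protocol violations (SAP 7.4): dose or frequency changes are named only for cholinesterase inhibitors.

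None supplies a window.

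**2. Timing.** The Summary gives "0 to 28 days for Screening, a 2-week Single-Blind Run-In Period to evaluate baseline status". For a drug started one day before Screening, days on drug at Baseline are:

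| | Shortest Screening (0 days) | Nominal schedule (Week -6) |
|---|---|---|
| As written | 1 + 0 + 14 = 15 | 1 + 42 = 43 |
| Under the 30-day rule | 30 + 0 + 14 = 44 | 30 + 42 = 72 |

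**3. The plan's own power figure.** Inputs from Protocol 10.2: difference 4, SD 7.5, 70 per arm, two-sided 0.05. In a two-sample t-test the noncentrality is 4 / (7.5 × √(2/70)) = 3.155 on 138 degrees of freedom, giving power 88.0%. The stated 88% is reproduced. At 80 per arm the noncentrality is 3.373 and power is 91.8%.

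**4. Effect of recent changers.** Let a share f of subjects gain a further X points after Baseline because of the earlier drug change.

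- Bias: f is the same in every arm in expectation, so the expected treatment difference is 4 + fX − fX = 4.
- Variance: SD = √(7.5² + f(1 − f)X²). For example, f = 10% and X = 8 gives √(56.25 + 0.09 × 64) = √62.01 = 7.87.

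The values of f and X are assumptions; the documents give neither.

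| f | X | SD | Power, 70 per arm | Power, 80 per arm |
|---|---|---|---|---|
| 5% | 2 | 7.51 | 87.9% | 91.7% |
| 5% | 4 | 7.55 | 87.5% | 91.5% |
| 5% | 8 | 7.70 | 86.3% | 90.4% |
| 10% | 2 | 7.52 | 87.8% | 91.7% |
| 10% | 4 | 7.60 | 87.2% | 91.2% |
| 10% | 8 | 7.87 | 84.7% | 89.1% |

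The largest loss at 70 per arm is 88.0 − 84.7 = 3.3 points. At 80 per arm, if all are analysed, power never falls below 88%.

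**5. A Baseline covariate.** With partial correlation r between anti-parkinsonian use at Baseline and the change score, SD = 7.5 × √(1 − r²). Assumed r of 0.1, 0.2 and 0.3 gives SD 7.46, 7.35 and 7.15, and power at 70 per arm of 88.3%, 89.2% and 90.7%.

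**The case against.** The strongest reply is that little is lost and much is already covered. Parkinsonism is a core feature of DLB, so a stable regimen of DLB therapy naturally includes motor drugs. New treatments are barred during the study, there is a run-in, the MMRM adjusts for baseline UPDRS-III and its interaction with visit, and the UPDRS populations deal with later increases. The documents do not say that a motor-drug response is still developing after 15 to 43 days, or that 30 days would be enough for these classes. Eight further points would be twice the 4-point target difference. The 15-day case needs a zero-length Screening, which is hard to achieve with laboratory results and, for some subjects, a scan outstanding. On the nominal schedule exposure is 43 days, one short of the 44-day minimum under the rule.

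Most of this stands, and it sets the severity. The 15-day case is an extreme on paper, and the loss is small on any of the inputs tried. Two things survive. The general wording leaves each site to decide what stable means for motor drugs, whereas other classes have a number. And 43 against 44 compares a nominal schedule with a minimum one; like for like, the rule adds 29 days (15 to 44, or 43 to 72).

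**Conclusion.** The gap is real. As written, the plan admits subjects whose motor drugs were started shortly before Screening, or whose dose change was completed by Baseline, and keeps them in the UPDRS-III analysis. Expected bias is zero. The cost is added variance: 0 to about 3 power points at 70 per arm, with power still above 88% if all 80 per arm are analysed. These sizes rest on an assumed 5-10% of subjects and 2-8 points of remaining response. If the SD of 7.5 already reflects such subjects, there is no loss. This is a low-severity improvement, worth making because it is cheap.

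Three stronger readings are not supported:

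- **That the treatment comparison is biased.** The drug change precedes randomisation, so only chance imbalance remains, and the variance calculation includes it.
- **That motor drugs may be freely started after Screening.** The Summary's bar on additional DLB treatments reasonably covers this.
- **That these subjects would be invisible.** SAP 8.6 counts as new-onset only drugs begun after the first double-blind dose, so no planned summary table isolates them. But SAP 7.3 provides listings of all CRF data with Study Day for date fields, so recorded starts can be found there.

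**What to change.** 1. **Close the gap.** For subjects not yet enrolled, add L-dopa, dopamine agonists and permitted MAO-B inhibitors to criterion 3 and to the conditional column of Table 1, under the existing 30-day pre-Screening rule, and require stability through Baseline. The cost is a short amendment and slightly slower enrolment of recently treated subjects. SAP 3 records that the safety committee's visit-frequency review has taken place, so enrolment was already under way; if it is complete, this step no longer applies.
2. **Separately, gain precision.** Before unblinding, add anti-parkinsonian use at Baseline (yes/no) to the UPDRS-III MMRM, and classify the SAP 7.8 subgroup at Baseline. The cost is one covariate and one classification date, using data already collected. This does not identify recent starters and does not itself close the gap.
3. **Optional.** Tabulate by arm the subjects whose regimen changed between 30 days before Screening and Baseline. Use recorded dates and show partial dates separately, because SAP 7.7.3 moves a start with a missing day to the first double-blind dose when the month and year match. Protocol 7.9.1 requires at minimum only drug name and dates, so dose changes will show only where dose was recorded.

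A rerun of the MMRM without these subjects is not worth adding. Starting from 70 per arm, removing 5% or 10% gives power of 86.3% or 84.4%, which beats keeping them only if the remaining gain exceeds about 8 points (8.0 and 8.4 respectively).
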